#### Pre-Visit/Baseline Survey

The pre-visit survey included several established scales and individual survey items. Upper GI symptoms were assessed using the Reflux Disease Questionnaire (RDQ), a validated PRO scale. Quality of life was assessed using the Short Form-12 (SF-12). We also included single items to assess baseline trust in PCP, concern about PPI-related harms, and receptiveness to de-prescribing of PPIs, all taken from an existing survey instrument.

#### Post-Visit Survey

For the 3-month follow-up survey, we again assessed symptoms and quality of life using the RDQ and SF-12, respectively. As a measure of “reach” for our process evaluation, we developed a single item to assess whether the patient recalls a discussion with the PCP about PPI de-prescription. Furthermore, we developed items to assess use of non-VA medications for symptom control (PPIs, H2RAs, antacids) and the use of non-VA healthcare. We also asked Veterans to report the source of payment for these services (e.g., out of pocket, private insurance).

## 8 STATISTICAL ANALYSES

We **hypothesized** that RaPPID will reduce the use of PPIs without a clinically meaningful increase in upper GI symptoms or upper GI complications such as bleeding.

**Primary outcome measure:** The **primary outcome** was the proportion of days PPIs are prescribed at or above the baseline daily dosing-frequency, over the 12 months following the index visit. We **hypothesized (H1)** that the proportion of days would be lower in intervention group than in the control group (i.e., that the outcome would be superior in the intervention vs control group). This outcome is analogous to the medication possession ratio. This was the appropriate measure of success of de-prescribing because it captured a variety of results in a single endpoint, including discontinuation without resumption, discontinuation with intermittent or on-demand use, and resumption of daily PPI at or above baseline dosing frequency. **Secondary outcome measures:** We also measured a variety of secondary outcomes to assess unintended, adverse events related to PPI de-prescribing. We hypothesize that utilization of outpatient care (H2) and the patient reported outcome (PRO) of upper GI symptoms (H3) will be non-inferior in the intervention vs control group.

**Utilization of outpatient and inpatient care:** Using CDW data, we assessed utilization of outpatient care – clinic visits or emergency department visits (using stop codes) for predefined upper GI symptoms/diagnoses (based on ICD-10 codes) or upper endoscopies (based on CPT codes). We also assessed use of inpatient care (i.e., hospital admissions) for predefined upper GI symptoms/diagnoses (based on ICD-10 codes).

**Upper GI symptoms and quality of life:** We assessed upper GI symptoms using the RDQ, a validated PRO instrument (30,31). We also measured generic quality of life using the SF-12 (32).

**Serious GI complications:** We assessed upper GI complications (bleeding, perforation, obstruction) using ICD-10 codes.

**PPI-related harms:** To ensure that we captured all relevant harms, we reviewed published observational studies of PPI harms to identify relevant diagnoses and ICD-9/10 codes.

**Covariates:** Covariates included demographics (age, sex, race/ethnicity), Charlson comorbidity index, indication for PPI use (uncomplicated GERD vs no indication), and baseline PPI dosing frequency (once-daily vs twice-daily). We also collected covariates on a subset of patients (1 intervention VISN and 1 control VISN), using our survey questionnaires, including baseline RDQ symptom score, trust in provider, baseline concern about PPI harms, and receptiveness to de-prescribing of PPIs.

### 8.1 SAMPLE SIZE DETERMINATION

[figure not shown]
#### 8.1.1 PRIMARY OUTCOME

Assuming approximately the same number of eligible subjects in each VISN (with an average of 10,563 candidates per VISN) and an ICC of 0.12, randomizing 17 VISNs will give more than 80% power to detect % days on PPI of 75% vs. 50%, 85% vs. 60%, 80% vs. 55%, or 70% vs. 45%, but to detect a difference between 70% vs. 50%, power is only 61% using 0.05 level 2-sided test.

[figure not shown]
#### 8.1.2 VETERAN SURVEYS

Recruitment numbers were based on a power calculation in which patient-reported symptoms, as measured by the Reflux Disease Questionnaire, were treated as a continuous variable rather. Based on previous research, we assumed an RDQ score Standard Deviation (SD)=1.3 for GERD patients for this calculation. To detect the between-group difference of 0.71 vs. 1.13, assuming SD=1.3 with 90% power and alpha=0.01, we need 287 surveys completed per group (574 in total) at 3 months and 820 in total surveys returned at baseline to account for 30% dropout by month 3. We estimated a 50% response rate for the baseline survey and a 70% response rate for the follow-up survey. we mailed 1,722 baseline surveys and approximately 850 follow-up (3 month) surveys.

### 8.1.3 FINAL REPORT UPDATE: RCT CONSORT DIAGRAM

8.1.4 FINAL REPORT UPDATE: SURVEYS CONSORT DIAGRAM

## 8.2 POPULATIONS FOR ANALYSES

- Intention-to-Treat (ITT) Analysis Population
- Repeated Measures
  - In addition to intent-to-treat, patient reported outcomes will be measured through surveys over time.

## 8.3 STATISTICAL ANALYSES

Analyses proceeded in 3 phases. In the 1st phase, we examined the distribution of all study variables to assess extreme values, missing data, variances, possible coding errors, skewness, and type of distribution. In the 2nd phase, we evaluated bivariate associations between study arm and outcomes, as well as between each covariate and outcomes, using generalized linear models with generalized estimating equations to account for clustering. This was done to determine unadjusted measures of effect, assess possible confounders, and anticipate any collinearity in subsequent analyses. In the final phase, we fit multivariable models to identify the effects of the intervention.

Primary outcome (H1): To assess the primary outcome (proportion of days PPIs are prescribed), we used an intent-to-treat analysis with a mixed-effects model, with proportion of PPI days over 12 months as the dependent variable. The primary independent variable was study arm. Because randomization was done at the VISN (regional) level, we anticipated that patients seen at the same facility will show a positive intraclass correlation (ICC). The mixed-effects model accounted for such clustering by including VISNs as random intercepts. It also controlled for VISN strata variables used in randomization. We did not account for patient dropout since all data collection is done electronically and does not require further patient participation.

To assess secondary outcomes (utilization of outpatient care and upper GI symptoms patient reported outcomes), we used generalized linear mixed-effects models with logit link (hierarchical logistic regression) to account for VISN-level clustering and randomization strata. The primary independent variable was study arm. For each outcome, an odds ratio (OR) for adverse events in the intervention group relative to the control group was obtained from each logistic regression model, where a significant OR less than 1.0 will favor the intervention group. For analyses of the patient reported outcomes, the outcome of interest was the RDQ score assessed at 3 months. For both outcomes, non-inferiority was assessed by comparing the effect estimate and its 90% CI with a non-inferiority margin.

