### 8.3.1 BASELINE DESCRIPTIVE STATISTICS

Intervention and control groups were compared on demographics of age, race, ethnicity, marital status, education, and Charlson Comorbidity Index (CCI).

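### Section 8.3 screens covariates against outcomes alongside the arm effect, and leaves open whether the strata-only or a covariate-adjusted model is the H1 test

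*Combined protocol and SAP*

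**What the plan says.** Section 8.3 describes three phases. The first checks distributions. The second relates study arm to the outcomes, and each covariate to the outcomes, with GEE models. Its purpose is stated as: "This was done to determine unadjusted measures of effect, assess possible confounders, and anticipate any collinearity in subsequent analyses". The third reads: "In the final phase, we fit multivariable models to identify the effects of the intervention". No covariate list and no selection rule is given for that phase.

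The next paragraph of section 8.3 gives a model for H1: an intention-to-treat mixed-effects model for the proportion of PPI days, with arm, VISN random intercepts and the strata used in randomization. It names no patient covariate.

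The Covariates paragraph of section 8 lists age, sex, race/ethnicity, the Charlson index, "indication for PPI use (uncomplicated GERD vs no indication), and baseline PPI dosing frequency (once-daily vs twice-daily"). It does not say which model these enter.

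For the primary outcome, section 8.1.1 plans "with an average of 10,563 candidates per VISN) and an ICC of 0.12". For 70% against 50% of days it reports that "power is only 61% using 0.05 level 2-sided test".

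**The concern.** The parts of the plan do not fit together. If the H1 paragraph is complete, the confounder screen and the covariate list have no stated role in H1. If they do have a role, the H1 model is not specified. The second phase also yields its own unadjusted arm effect from GEE, a different estimator from the H1 mixed model, and nothing ranks the two.

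In a randomized comparison, covariates are best fixed in advance for their prognostic value. Screening them on the outcome adds nothing to validity and can discard useful ones. Because the arm effect appears in the same phase, a reader of the results cannot tell whether the reported model was settled before that effect was seen. The document does not resolve this. It is dated 28 May 2019, but it describes the analyses in the past tense and carries final-report updates in sections 9.2 and 9.4.

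At stake are the clarity of the single H1 test and the precision that a fixed covariate set could add in a trial with few clusters.

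**Working it through.** **Inputs.** From section 1.2: 9 intervention and 8 control VISNs. From section 8.1.1: 10,563 candidates per VISN, ICC 0.12, two-sided 0.05, and 61% power for 70% against 50%. The share of between-VISN outcome variance explained by the covariates (R2) is not in the documents. It is an assumption, varied from 0 to 0.7.

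**1. Reproducing the plan's 61%.**
- Design effect: 1 + (10,563 − 1) × 0.12 = 1,268.4.
- Effective patients per VISN: 10,563 / 1,268.4 = 8.33.
- 8 against 8 VISNs, unpooled variance: SE = √[(0.70×0.30 + 0.50×0.50) / (8×8.33)] = 0.0831. Noncentrality 0.20 / 0.0831 = 2.407. Noncentral t on 14 df gives 61.0%.
- 9 against 8 VISNs, pooled variance: SE = √[0.60×0.40×(1/(9×8.33) + 1/(8×8.33))] = 0.0825. Noncentrality 2.425. Noncentral t on 15 df gives 62.1%.

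The stated figure is reproduced with a t reference. A normal approximation gives 68.4% and does not match. The four 25-point scenarios give 80.1% to 87.4% with the pooled t on 15 df, as the plan says.

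**2. Type I error under different ways of choosing the model.** Null VISN-level data were simulated with 9 against 8 VISNs, a t reference, strata ignored and 40,000 to 60,000 runs per setting.

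| Procedure | Type I error at nominal 5% |
|---|---|
| One model fixed in advance, adjusted or not | 4.9% to 5.3% |
| Covariates kept on association with outcome only | 4.9% to 5.2% |
| Smaller p of unadjusted and adjusted, R2 = 0.1 | 6.5% to 6.9% |
| Same, R2 = 0.3 | 7.4% to 7.8% |
| Same, R2 = 0.5 | 8.2% to 8.5% |
| Same, R2 = 0.7 | 8.8% to 8.9% |

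With 60 or 130 clusters, taking the smaller p gives 6.6% to 6.7%, 7.5% to 7.8% and 8.3% to 8.5% for R2 of 0.1, 0.3 and 0.5. The number of clusters hardly matters.

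**3. Power with a fixed adjusted model.** The variance of a VISN mean is almost wholly between VISNs: 0.12 / (0.12 + 0.88/10,563) = 0.999. If the covariates explain a share R2 of it, the noncentrality is divided by √(1 − R2). Coefficients estimated from thousands of patients cost essentially no VISN-level degrees of freedom.

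| R2 (assumed) | Noncentrality, 8 v 8 | Power, 8 v 8 | Noncentrality, 9 v 8 | Power, 9 v 8 |
|---|---|---|---|---|
| 0 | 2.407 | 61.0% | 2.425 | 62.1% |
| 0.1 | 2.537 | 65.6% | 2.556 | 66.6% |
| 0.2 | 2.691 | 70.7% | 2.711 | 71.7% |
| 0.4 | 3.107 | 82.3% | 3.130 | 83.3% |

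**The case against.** The best defence is that the H1 model is stated. The H1 paragraph follows the phased description, is specific to H1, and offers no choice between adjusted and unadjusted results. Arm plus strata is already a multivariable model, so the third phase need not contradict it. Read as binding, that paragraph removes the ambiguity, and one sentence saying so would be enough to protect the error rate. This stands as a fair reading. It does not explain why covariates are screened as possible confounders, or what the section 8 list is for.

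A reader might infer something stronger: that the model is chosen with the arm result in view, so that the 5% test fails, and that having only 17 VISNs is the cause. The documents do not support this. No text says that the arm result drives the choice, although none rules it out. The screen that is described, covariate against outcome, keeps about 5%. The inflation in the table requires an analyst to report the smaller of two p-values, and searching covariate subsets for the best arm result would go further still. The plan describes neither. Nor is the inflation tied to 17 clusters.

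It is also fair to say that preferring a covariate-adjusted model over the strata-only model is a matter of precision. Either one, fixed in advance, holds 5%.

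**Conclusion.** The plan does not reconcile its confounder screen and covariate list with its H1 model, so the identity of the H1 test is left open. This is a gap in specification, not a demonstrated error in the 5% level. The conditional risk is about 6.5% to 9% if the more favourable of two results were reported, for an assumed R2 of 0.1 to 0.7.

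The positive case for change is precision. In the plan's 61% scenario, a fixed adjusted model would give about 66% to 82% power for an assumed R2 of 0.1 to 0.4. That rests on three further assumptions: a t reference, which the plan does not name; strata ignored; and covariate relations within VISNs that also account for the differences between them. The actual R2 is unknown, so the gain could be smaller. The point concerns H1 only.

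**What to change.** In section 8.3, limit the second phase to description and remove the assessment of confounders as a purpose for H1. State one primary H1 model: arm, randomization strata, VISN random intercept, and age, sex, race/ethnicity, Charlson index, indication and baseline dosing frequency, all kept whatever their p-values. Label the strata-only model supportive.

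Indication cannot stay two-level. Section 5.1 admits twice-daily users with any indication except Zollinger-Ellison, and the categories of uncomplicated GERD and no indication cannot classify all of them. A further level is needed. The survey-based covariates exist in only two VISNs and should stay out of the H1 model.

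If arm-level results have already been seen, state which model was fixed beforehand and when, and report both.

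The cost is wording, since the listed covariates are already held in CDW. What is lost is the freedom to choose the model later.

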# 5 STUDY POPULATION

## 5.1 INCLUSION CRITERIA

The target population was chronic proton pump inhibitor (PPI) users who had a scheduled primary care visit.

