### 7.2.1 VARIABLES & DATA SOURCES

Variable	Description	Time Frame	Data Source
Primary Outcome			
PPI de-prescribing	Proportion of days PPI prescribed after index visit ( H1 )	12 mo	CDW
Secondary Outcomes			
Utilization of outpatient care	Outpatient visit, ED visit, or upper endoscopy (EGD) for: (1) upper GI symptoms/conditions; (2) any cause	12 mo	CDW
Utilization of inpatient care	Hospital admission for: (1) upper GI symptoms/conditions; (2) any cause	12 mo	CDW
Serious GI complications	Complications of peptic ulcer disease (bleeding, obstruction, perforation)	12 mo	CDW
PPI-related harms	E.g., fractures, enteric infections, pneumonia, kidney disease, dementia	12 mo	CDW
Upper GI symptoms	Upper GI symptoms (RDQ)	0, 3 mo	Surveys
Cost	Healthcare expenditures related to VA and non-VA care	24 mo	Calculated
Reach	Proportion of patients offered de-prescribing	3 mo	Post Survey
Adoption	Reduction in PPI use before / after program deployment	3, 12 mo	CDW
Implementation	Implementation fidelity and consistency at each site (process)	3, 12 mo	Staff Interviews

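### Outpatient utilization is modeled only as any use versus none; for its any-cause version the odds ratio does not quantify a change in visits and can support non-inferiority while visits per patient rise

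*Combined protocol and SAP*

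**What the plan says.** Section 8 states the hypothesis: "We hypothesize that utilization of outpatient care (H2) and the patient reported outcome (PRO) of upper GI symptoms (H3) will be non-inferior". The same section describes outpatient utilization as "clinic visits or emergency department visits (using stop codes) for predefined upper GI symptoms/diagnoses (based on ICD-10 codes) or upper endoscopies" and does not mention any-cause visits.

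The Section 7.2.1 table gives the outcome a wider scope, over 12 months from CDW: "Outpatient visit, ED visit, or upper endoscopy (EGD) for: (1) upper GI symptoms/conditions; (2) any cause".

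Section 8.3 provides one method for this outcome: "we used generalized linear mixed-effects models with logit link (hierarchical logistic regression) to account for VISN-level clustering and randomization strata". The result is expressed as follows: "an odds ratio (OR) for adverse events in the intervention group relative to the control group was obtained". The event itself is not defined, and no count or rate model for utilization appears anywhere. The decision rule is that "non-inferiority was assessed by comparing the effect estimate and its 90% CI with a non-inferiority margin", with no numeric margin.

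Section 5.1 defines the target population as "chronic proton pump inhibitor (PPI) users who had a scheduled primary care visit". The documents do not say whether that index visit counts toward utilization, and they give no outpatient visit rates.

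**The concern.** A logistic model needs a yes/no outcome, and the natural reading here is at least one visit in 12 months. Applied to any-cause visits in patients who are in active primary care, such an indicator has two weaknesses.

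- Most patients in both arms are likely to be positive whatever the program does, so the indicator carries little information about how much care they use.
- A patient who would have had one visit and now has three contributes nothing to the comparison. Repeat visits are one of the ways in which worse symptoms would show.

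H2 is a non-inferiority hypothesis about an unintended consequence of de-prescribing. An outcome that does not register added visits pulls the comparison toward no difference, which is the conclusion the hypothesis favors.

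**Working it through.** The plan states no rate, power or sample size for H2, so there is no figure of its own to reproduce. The visit means, the size of the rise and the dispersion values below are all assumptions.

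**1. Any-cause visits, uniform 25% rise.** Let visits follow a negative binomial with mean μ and dispersion α. Then

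P(no visit) = (1 + αμ)^(−1/α), which becomes exp(−μ) as α goes to 0,

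and the odds of at least one visit are [1 − P(no visit)] / P(no visit). Take μ = 5 in control and 5 × 1.25 = 6.25 in intervention, so the rate ratio is 1.25 in every row.

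| α | P(no visit), control | P(no visit), intervention | At least one visit | Change, points | Odds ratio |
|---|---|---|---|---|---|
| 4 | 21^(−0.25) = 0.467 | 26^(−0.25) = 0.443 | 53.3% to 55.7% | 2.4 | 1.10 |
| 1 | 1/6 = 0.167 | 1/7.25 = 0.138 | 83.3% to 86.2% | 2.9 | 1.25 |
| 0.5 | 3.5^(−2) = 0.0816 | 4.125^(−2) = 0.0588 | 91.8% to 94.1% | 2.3 | 1.42 |
| 0 | exp(−5) = 0.0067 | exp(−6.25) = 0.0019 | 99.3% to 99.8% | 0.5 | 3.5 |

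The same rise in use gives odds ratios from 1.10 to 3.5. The odds ratio equals the rate ratio only at α = 1, where the odds equal μ. It understates the rise when dispersion is above 1 and overstates it when dispersion is below 1. Leaving sampling error aside, any margin between 1.10 and 3.5 would accept this rise under one dispersion and reject it under another.

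**2. Rise confined to patients who would attend anyway.** The share with at least one visit is then the same in both arms, so the odds ratio is exactly 1.0, while mean visits go from 5 to 6.25.

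**3. Dilution of an upper GI effect by other visits.** Suppose the share with an upper GI visit rises from 10% to 12%. For upper GI visits alone, the odds ratio is (0.12/0.88) / (0.10/0.90) = 1.23. Now let the event be any visit for any cause, with a control share p, and let upper GI and other visits be independent. Then P(no visit) in the intervention arm is (1 − p) × 0.88/0.90.

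- p = 90%: 90.0% to 90.2%, odds ratio 1.025
- p = 95%: 95.0% to 95.1%, odds ratio 1.024
- p = 98%: 98.00% to 98.04%, odds ratio 1.023

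**4. Upper GI visits only.** With μ = 0.15 a year and the same uniform 25% rise, the odds ratio is 1.20 at α = 4, 1.25 at α = 1 and 1.27 at α = 0. The share with a visit starts at 11% to 14%. There is no ceiling, and the odds ratio stays close to the rate ratio. What is still lost is repeat visits by patients who would have had an upper GI visit anyway.

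**The case against.** The strongest objection concerns scope. A reader might infer from the Section 7.2.1 table that H2 is a test of any-cause visits. The documents do not support that. Section 8, where H2 is stated, describes only upper GI visits and endoscopies, and the reference in Section 8.3 to adverse events fits a yes/no upper GI event. This stands: for that version the binary model is workable, as step 4 shows, and replacing it would be a preference. The table nevertheless lists any-cause visits under the same outcome name, and Section 8.3 gives that outcome no other model.

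A reader might also infer that the odds ratio is itself saturated and cannot detect a change. That does not follow. The proportion may approach its ceiling, but in step 1 the odds ratio is 1.25 or more whenever dispersion is 1 or less. The understatement needs dispersion above 1, a rise concentrated in existing attenders, or dilution as in step 3. At dispersion 4 the proportion is about 53%, well short of a ceiling.

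Finally, a reader might infer that every patient is positive because all have an index visit. Section 5.1 requires a scheduled visit; neither attendance nor the counting of that visit is stated.

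The absence of a numeric margin and the undefined event are real gaps, but separate ones.

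**Conclusion.** The point holds for the any-cause version of outpatient utilization. A yes/no analysis of those visits does not quantify a change in use: under the assumed mean of 5 visits a year, one 25% rise corresponds to odds ratios from 1.10 to 3.5. It can also support non-inferiority while visits per patient rise, most plainly when the rise falls on patients who would attend anyway and the odds ratio stays at 1.0. That most patients would have an any-cause visit is likely given how they were identified, but it is an inference. The share is about 83% to 99% for dispersion 1 to 0, and lower with more dispersion.

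The point does not extend to upper GI visits at low rates, where only the loss of repeat visits remains. It concerns a secondary hypothesis, but one about an unintended consequence of the program, so the change should be made.

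**What to change.** - Analyze any-cause outpatient visits as counts over the 12 months after the index visit, excluding that visit, in a negative binomial mixed model with a VISN random intercept and the randomization strata. Judge non-inferiority for this outcome on the rate ratio.
- Keep the logistic model for upper GI visits, ED visits and upper endoscopy. Add a count model of upper GI visits as a sensitivity analysis for repeat visits.
- Reconcile Sections 7.2.1 and 8, and state which scope H2 tests.

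The cost is a change of wording in Section 8.3 and one additional model, plus the sensitivity analysis, on data already extracted from CDW. If the analyses are complete, report the count model as a labelled sensitivity analysis.

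### Section 8.3 analyses the 3-month RDQ score (H3) by logistic regression with no defined event, and claims a VISN and strata adjustment that one surveyed VISN per arm cannot support

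*Combined protocol and SAP*

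**What the plan says.** Section 8 states H3 as non-inferiority of the intervention on patient-reported upper GI symptoms. Section 8.3 then assigns both secondary outcomes, outpatient utilization (H2) and symptoms (H3), to "generalized linear mixed-effects models with logit link (hierarchical logistic regression) to account for VISN-level clustering and randomization strata". The effect measure is given as follows: "an odds ratio (OR) for adverse events in the intervention group relative to the control group was obtained from each logistic regression model". For the patient-reported analysis, "the outcome of interest was the RDQ score assessed at 3 months". The decision rule for both outcomes is that "non-inferiority was assessed by comparing the effect estimate and its 90% CI with a non-inferiority margin".

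Three other parts of the document bear on H3:

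- Section 8.1.2 sizes the survey on a different scale: "patient-reported symptoms, as measured by the Reflux Disease Questionnaire, were treated as a continuous variable rather" (the sentence breaks off there). The inputs are stated as "To detect the between-group difference of 0.71 vs. 1.13, assuming SD=1.3 with 90% power and alpha=0.01", giving 287 completed surveys per group.
- Section 8.2 lists repeated measures and says that "patient reported outcomes will be measured through surveys over time". Section 6.3 describes a longitudinal mixed-effects model that includes baseline predictors of missingness, with multiple imputation as a secondary analysis if more than 20% of data are missing.
- Sections 1.2, 7.2.2 and 8 (Covariates) confine the surveys to two VISNs, one per arm. Section 7.2.2 says that the intervention VISN was chosen because its Dashboard use was highest, and that the control VISN was chosen to be comparable.

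**The concern.** A logistic model needs an event. The RDQ score is not one, and neither section 8 nor the variables table in 7.2.1 turns it into one. An analyst following 8.3 would have to invent a cut-off, and the odds ratio, the power and the meaning of any margin would all depend on that choice. The document therefore holds three descriptions of the H3 analysis (logistic at 3 months, comparison of means, longitudinal mixed model) and does not say which one decides.

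The clustering wording raises a separate problem. It tells the reader that the H3 interval allows for variation between VISNs and for the randomization strata. With one VISN surveyed in each arm, no model can do that. H3 is the direct patient-reported check that de-prescribing does not worsen symptoms, so a reader needs to know what its interval does and does not cover.

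**Working it through.** **1. Reproduce the survey size.** Inputs from 8.1.2: difference 1.13 − 0.71 = 0.42, SD 1.3, power 90%, alpha 0.01.

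- Normal formula, two-sided: n = 2 × 1.3² × (2.576 + 1.282)² / 0.42² = 285.1, so 286 per group.
- Two-sample t-test, two-sided: 286.8, so 287 per group. This matches.
- One-sided: 250. This does not match.
- Baseline returns: 574 / 0.70 = 820. This matches.

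The stated size is thus a two-sided comparison of means on independent patients, with no clustering term. The arithmetic is correct.

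**2. Put the same assumptions through a dichotomised score.** Cut-offs and distributions here are assumptions. No odds-ratio margin is stated, so the calculation is a difference test at 8.1.2's alpha. With p1 and p2 the proportions above the cut and p̄ their mean,

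power = Φ{[(p2 − p1) − 2.576 √(2p̄(1 − p̄)/287)] / √([p1(1 − p1) + p2(1 − p2)]/287)}.

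| Cut | Normal: p1, p2 | OR | Power | Gamma, same means and SD: p1, p2 | OR | Power |
|---|---|---|---|---|---|---|
| 0.92 | 0.436, 0.564 | 1.68 | 0.692 | 0.228, 0.413 | 2.38 | 0.986 |
| 2.0 | 0.161, 0.252 | 1.76 | 0.549 | 0.106, 0.179 | 1.83 | 0.465 |
| 3.0 | 0.039, 0.075 | 2.00 | 0.237 | 0.058, 0.086 | 1.52 | 0.098 |

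Under normality 0.92 is the best cut, so about 70% is the ceiling. One shift of 0.42 RDQ points corresponds to odds ratios from about 1.5 to 2.4, and power runs from 10% to 99%. An odds-ratio margin has no fixed meaning in RDQ points until the cut-off is stated.

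**3. Count what the surveyed VISNs can identify.** Two clusters minus two arm means leaves 0 degrees of freedom for between-VISN variance. Equivalently, a design with an intercept, an arm indicator and two VISN indicators has 4 columns and rank 2. A VISN-level stratum variable is constant within each arm, so it is either the same in both arms or identical to the arm contrast. Neither effect can be separated from arm. This needs no assumed ICC.

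**4. Illustrate the consequence for the 90% CI.** Ignoring VISN, SE0 = 1.3 × √(2/287) = 0.1085 and the half-width is 1.645 × 0.1085 = 0.18 RDQ points (unadjusted for baseline). If VISNs are treated as random draws, the true SE = 1.3 × √{2[(1 − ICC)/287 + ICC]}. When the true difference equals the margin, the false non-inferiority rate is Φ(−1.645 × SE0/SE).

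| Assumed RDQ ICC | True SE | False non-inferiority (nominal 5%) | Coverage of the 90% CI |
|---|---|---|---|
| 0.001 | 0.123 | 7.3% | 85% |
| 0.005 | 0.169 | 14.6% | 71% |
| 0.01 | 0.213 | 20.1% | 60% |

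The document gives no RDQ ICC. The 0.12 in 8.1.1 is for the primary outcome only.

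**The case against.** **The continuous model may already be there.** Section 6.3 describes a longitudinal mixed model and 8.2 lists repeated measures, so the remedy need not be a new model. That stands. However, 6.3 gives no link function and 8.3 does not refer to it, so the conflict remains.

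**A binary RDQ outcome may have been intended.** The sentence in 8.1.2 that breaks off concerns the power calculation and could point to one. Even so, none is defined.

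**The power loss depends on the distribution.** A normal score with SD 1.3 puts Φ(−0.71/1.3) = 29% of one group and Φ(−1.13/1.3) = 19% of the other below zero, which is implausible for a symptom score. Under the gamma alternative, a cut at 0.92 gives 99% power. The 70% ceiling therefore holds only under normality. The undefined event does not depend on any distribution.

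**The selection of VISNs is disclosed.** Section 7.2.2 states it openly, so the gap in 8.3 is one of interpretation and not concealment.

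**Non-inferiority need not be easier to claim.** A reader might infer that the plan makes a false claim of safety likely. The documents do not support that as a finding. The rates in step 4 rest on assumed ICCs and treat two purposively chosen VISNs as random draws. Surveying the most active VISN could also expose more patients to de-prescribing and make worsening easier to see. The direction of any bias is unknown.

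**Conclusion.** Wrong as written and should be fixed, for a secondary outcome. Two conclusions need no assumed values. The H3 logistic analysis has no defined event and does not match the comparison the survey was sized for or the longitudinal analysis in 6.3 and 8.2. The statement that the model accounts for VISN clustering and strata cannot be true for H3, so an H3 interval estimated from these data excludes between-VISN variation. H3 is a comparison of two selected VISNs, not a randomized cluster comparison.

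The sizes are conditional. Power of at most about 70% after dichotomising assumes normal scores. The interval is too narrow only if between-VISN variation is not zero, and the range of 7% to 20% against 5% depends on the assumed ICCs and on treating the VISNs as random draws.

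Two further inferences should be resisted: that the survey size is miscalculated (it reproduces) and that the mixed model is unsuitable for H2 (with 17 VISNs the clustering term can be estimated).

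**What to change.** 1. Analyse H3 on the continuous RDQ scale used in 8.1.2, adjusted for the baseline RDQ score already collected. Reconcile 6.3, 8.2 and 8.3 by naming one primary model: either the longitudinal mixed model of 6.3 or a baseline-adjusted linear model. Keep the multiple-imputation analysis of 6.3 when missingness exceeds 20%; 8.1.2 itself anticipates 30% dropout. Express the non-inferiority margin in RDQ points. Any logistic analysis becomes supportive, with its cut-off stated.
2. The document is written retrospectively, and 6.2 says there was no blinding after randomization. Cite a dated record from before the data were seen for each of the model, the scale and the margin, or label each one post hoc. This applies to the replacement model as much as to the margin.
3. For H3, delete the claim that the model accounts for VISN clustering and strata. State that one selected VISN per arm was surveyed, that the H3 interval and power exclude between-VISN variation, and that H3 is not a randomized cluster comparison. Optionally, show intervals under a range of assumed ICCs.
4. Leave the H2 model unchanged.

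The cost is revised wording in 8.3 with cross-references to 6.3 and 8.2, a search for dated records, and one re-analysis of survey data already in hand. No new data are needed. The choice of surveyed VISNs cannot be undone, only described accurately.
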